7.2.2.2 Recording of Angioedema Attacks in the Electronic Subject Diary

During the study, subjects will use an electronic subject diary each day to record any symptoms or occurrences of an angioedema attack. The investigator will complete a separate angioedema attack CRF for each attack based upon their review of the data in the subject diary. Information will include the following:

- Date and time of onset and complete resolution of angioedema attack symptoms
- Characterization of whether swelling or pain is (indicate all that apply):
 - Mucosal (pharyngeal, laryngeal, gastrointestinal, genitourinary)
 - Non-mucosal (truncal, extremity, facial)
- Location (site) of the swelling or pain (indicate all that apply):
 - Upper airway (includes laryngeal or pharyngeal)
Note: Pharyngeal or oral swelling that results in airway compromise will be classified as a laryngeal attack.
 - Gastrointestinal/abdominal (including symptoms of pain, nausea, vomiting, swelling, and/or change in bowel habits)
 - Genitourinary (including scrotum or vulva)
 - Cutaneous (facial)
 - Cutaneous (extremity, peripheral, or torso [eg, buttocks, external head/neck, trunk])
- Severity (intensity) of the sign/symptom at each location listed:
 - Absent
 - Mild: the angioedema attack sign/symptom(s) is noticeable but is easily tolerated by the subject and does not interfere with routine activities.
 - Moderate: the angioedema attack sign/symptom(s) interferes with the subject's ability to attend work/school or participate in family life and social/recreational activities.

- Severe: the angioedema attack sign/symptom(s) significantly limits the subject's ability to attend work/school or participate in family life and social/recreational activities.
- Visual Analogue Scale (VAS) pain measurement score
- Angioedema attack trigger(s)
- Answer to the question, "Was treatment administered for the attack?" If yes, record the date, time, and name of treatment administered.

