10.4 Other Secondary Efficacy Variable(s) and Analysis

Data from subjects in the Full Analysis Set that are randomized to Treatment Sequence 1 (A/B) or 2 (B/A) will be used to assess the secondary efficacy endpoints in the evaluation of the efficacy of SC administration of C1 esterase inhibitor [human] liquid for injection compared to placebo. If a subject discontinues during the treatment period, the days of the treatment period will be the days on treatment for that subject; this is equivalent to the last observation carried forward imputation method to impute the missing information following the subject's discontinuation.

Other secondary efficacy variables are listed as following:

- To determine the proportions of subjects with a clinical response to treatment as defined by: Achieving at least a 50%, 70%, 90% and 100% reduction as well as subjects achieving reduction to less than 1 NNA during a treatment period relative to the pretreatment assessment.
- The summary of clinical response to treatment will be repeated using the Per-protocol Set
- Cumulative attack severity: the normalized sum (per month) of the maximum symptom severity recorded for each angioedema attack in a treatment period.
- Cumulative daily severity: the normalized sum (per month) of the severity scores recorded for every day of reported symptoms in a treatment period.
- Number of attack-free days during a treatment period: the normalized number (per month) of attack-free days.
- Number of angioedema attacks requiring acute treatment during a treatment period: the normalized number of angioedema attacks requiring acute treatment.
- Disease activity as measured by the 98-day AAS: the normalized sum of the daily AAS during a treatment period, where the daily AAS is the sum of AAS items per day. Each AAS item is scored between 0 and 3 points, with the minimum and maximum daily AAS ranging between 0 and 15 points.
- Results of the AE-QoL questionnaire: the questionnaire consists of 17 specific questions that are associated with work, physical activity, free time, social relations, and food.
- Number of angioedema attacks requiring icatibant by the number of icatibant injections during the first three attacks of the treatment period.
- Kaplan-Meier estimate of time to initial improvement and time to complete resolution since acute treatment administration by attack order during the treatment period.

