17.11 Handling Missing HAE Attack Data

If there are incomplete attack start/end dates in the collected data, the following imputations will be performed in a sequential order of the incomplete dates within each subject. This is to ensure that multiple identical incomplete dates will be imputed as separate attacks.

- Imputation of start date for an attack:
- If the attack start day is unknown and there is no previous attack in the same month, the first day of the month will be assigned to the missing field.
- If the attack start day is unknown and there is at least one previous attack in the same month, the previous attack end date + 1 will be assigned to the missing field.
- Imputation of end date for an attack:

The imputation of end date for an attack will follow one of the following 3 rules, whichever is the earliest:

- The start date of the current attack + 6 if attack end date is partially or completely missing.
- The start date of the next attack -2 if attack end date is partially or completely missing.
- The last day of the month if attack end date is partially missing with missing day only.

Page 54

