19. APPENDIX

19.1 Derivations of efficacy endpoints related to angioedema attacks

The derivations of efficacy endpoints are demonstrated using the following hypothetical example.

Study Day	Symptoms Present	Maximum ^a Symptom Severity	Symptom Severity Score	Attack Number	Maximum ^b Attack Severity	Daily Severity
1	Yes	Moderate	2	1	-	2
2	Yes	Moderate	2		2	2
3	No					
4	Yes	Mild	1	2	-	1
5	Yes	Severe	3		-	3
6	Yes	Moderate	2		3	2
7	No					
8	Yes	Moderate	2	3	-	2
9	Yes	Severe	3		-	3
10	Yes	Moderate	2		-	2
11	Yes	Moderate	2		3	2

a: Maximum Severity across all anatomic locations on the corresponding study day.

b: Maximum Severity across all anatomic locations and days with symptoms for the corresponding attack.

In this hypothetical example, a patient recorded 9 days of symptoms in an 11-day study period. Because individual attacks require at least one symptom-free calendar day between episodes, this diary fragment identifies 3 angioedema attacks. The maximum severity of each attack is determined on the last day of symptoms and is derived as Mild, Moderate, or Severe. Coding these categories as Mild=1, Moderate=2, and Severe=3 and summing over the three unique attacks, yields a Cumulative Attack Severity of 8. Finally, summing the reported severity scores over the 9 days with symptoms yields a Cumulative Daily Severity of 19. With respect to these defined endpoints, this hypothetical eleven-day symptom diary would be quantitatively described by:

Endpoint	Value
Number of Angioedema Attacks	3
Cumulative Attack Severity	8
Cumulative Daily Severity	19

For the secondary efficacy variables of Cumulative Attack Severity, Cumulative Daily Severity, Number of attack-free days during a treatment period, Number of angioedema attacks requiring acute treatment during a treatment period and 98-day AAS, the normalized numbers (per month) calculated by following steps will be used in the analyses.

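### SAP 17.11 imputes missing attack end dates without using the daily diary and can end an attack before its recorded end month; any effect on attack-free days has unknown direction

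*SAP*

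**What the plan says.** SAP 17.11 introduces its end-date rule with "The imputation of end date for an attack will follow one of the following 3 rules, whichever is the earliest". There are three candidates:

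- A ceiling of seven calendar days, worded as "The start date of the current attack + 6 if attack end date is partially or completely missing".
- A limit set by the following attack, two days ahead of its onset, under the same condition on the missing date.
- A calendar limit for partial dates, worded as "The last day of the month if attack end date is partially missing with missing day only".

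The diary is not mentioned. The month end is only an upper limit; nothing stops the imputed date from falling before the month that was recorded.

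A day-level record exists. Protocol 7.2.2.2 says that "subjects will use an electronic subject diary each day to record any symptoms or occurrences of an angioedema attack", and the investigator fills in the attack CRF from that diary, including the date and time of complete resolution. SAP 19.1 works from daily symptom rows: it concludes that "this diary fragment identifies 3 angioedema attacks" and sums daily severity over symptomatic days only.

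SAP 10.4 lists the endpoint as "Number of attack-free days during a treatment period: the normalized number (per month) of attack-free days" and analyses it with a mixed model. Neither 10.4 nor the appendix says whether those days are counted from attack dates or from diary rows. SAP 10.4 also plans Kaplan-Meier estimates of time to complete resolution, with no censoring.

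**The concern.** A fixed window is put in place of information that the diary may already hold. If attack-free days are counted from attack dates, an over-long imputed attack turns symptom-free diary days into attack days. Cumulative daily severity, which uses reported symptom days only, would treat the same days as symptom-free, so two endpoints could disagree about one diary.

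Separately, taking the earliest date can override something the site did record, namely the end month. That is a logic error whatever the amount of missing data.

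At stake are one other secondary endpoint with a treatment comparison and, possibly, the time-to-resolution estimates. The primary endpoint counts attacks, and an imputed end date does not by itself change that count.

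**Working it through.** **Inputs.** The three limits come from SAP 17.11, the diary example from SAP 19.1 and the 98-day period from SAP 10.5.2. The share of attacks with a missing end date (m, by arm) and their true duration (D days) are not in the documents, so both are assumed and varied.

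**1. Reproduce the 19.1 example.** Symptoms fall on days 1–2, 4–6 and 8–11.

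- Attacks: 3.
- Cumulative attack severity: 2 + 3 + 3 = 8.
- Cumulative daily severity: (2+2) + (1+3+2) + (2+3+2+2) = 19.
- Symptom days: 9 of 11.

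All agree with the SAP.

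**2. Apply 17.11 to that diary as if each end date were completely missing.**

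- Attack 1: min(1 + 6, 4 − 2) = day 2; last symptom day 2.
- Attack 2: min(4 + 6, 8 − 2) = day 6; last symptom day 6.
- Attack 3, if no later attack followed: 8 + 6 = day 14; last recorded symptom day 11, so 3 days too long.

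Seven calendar days is therefore a ceiling, reached only when neither a later attack nor the month end binds first.

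**3. Recorded-month conflict.** Start 15 March, end recorded as April with the day unknown: min(21 March, 30 April) = 21 March. The attack must have lasted at least from 15 March to 1 April, which is 18 days, but is given 7. In general, start + 6 can precede the recorded month only if the true end is at start + 7 or later, so the true duration is at least 8 days. This defect always shortens the attack.

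**4. Size and sign, if attack-free days use the imputed dates.** Where start + 6 applies, each affected attack changes the count of attack days by 7 − D. The shift in the active-minus-placebo difference, per month and before the next-attack limit, is

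(m_placebo × NNA_placebo − m_active × NNA_active) × (7 − D).

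With attack rates of 3 versus 2 per month:

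| Missing share, placebo / active | D = 2 | D = 3 | D = 7 | D = 9 |
|---|---|---|---|---|
| 5% / 5% | (0.15 − 0.10) × 5 = +0.25 | +0.20 | 0 | −0.10 |
| 5% / 10% | (0.15 − 0.20) × 5 = −0.25 | −0.20 | 0 | +0.10 |

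The next-attack limit shrinks these figures for short attacks. A simulation with that limit used 4,000 periods of 98 days per arm, fixed duration, about 3 versus 2 attacks per month and 5% missing in both arms:

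| D | Shift, days per month |
|---|---|
| 2 | +0.11 (true difference 2.16) |
| 3 | +0.09 (true difference 3.23) |
| 5 | +0.05 |
| 7 | 0 |
| 9 | −0.09 |

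For 2- and 3-day attacks that is 0.11/2.16 = 5% and 0.09/3.23 = 3% of the true difference.

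**The case against.** **The endpoint may not use these dates.** SAP 19.1 works from diary rows. If attack-free days are counted the same way, 17.11 has no effect on them. This stands: the link is an inference, and the SAP leaves it open.

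**Missing end dates may occur where the diary is also missing.** The attack CRF is completed from the diary, and Protocol 9.2 has omissions queried. If the diary shows the end, the CRF should too. This also stands in part: it limits how often the diary can help. It does not excuse the month conflict, where the rule discards information that was collected.

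**A reader might infer that the rule inflates the treatment difference in attack-free days**, because placebo has more attacks to extend. The documents do not support that. It assumes that the endpoint uses imputed dates, that the affected attacks are shorter than the imputed length, and that they are not more numerous on active. None of this is given. The month conflict works on long attacks and shortens them, which with equal missingness narrows the difference. With twice the missing share on active, the sign for short attacks reverses.

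**Conclusion.** The point holds as a defect in the imputation rule, not as a demonstrated bias. On its face, 17.11 does not use the diary and can produce an end date that contradicts the recorded month.

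Any effect on attack-free days or time to complete resolution depends on those analyses using the imputed dates. Over-extension would widen the attack-free-day difference only if attacks with missing end dates are truly shorter than imputed and are not more numerous on active. The direction is therefore unknown. About 0.1 day per month is the size for 2- to 3-day attacks under the equal 5% missingness assumed above; it is not an estimate from trial data.

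The consequences are limited: SAP 10.3 confines the test hierarchy to the primary and the three key secondary endpoints, and attack-free days is not among them. The change is still worth making because it is cheap and does not depend on the sign of the bias.

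**What to change.** Amend SAP 17.11 and the derivation appendix as follows.

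1. Set a missing end date to the last consecutive symptomatic diary day of that attack. Use the existing windows only where the diary days are also missing.
2. When the end month is recorded, do not impute a date before the first day of that month.
3. When the next attack's start is itself imputed, place it so that one symptom-free calendar day remains between the attacks. Without this, the floor in item 2 could overlap a next attack whose start has been imputed to the first of the same month. The current start rule, which uses the day after the previous attack's end, leaves no symptom-free day although Protocol 7.2.2.1 requires one for a new attack.
4. State that attack-free days are counted from diary symptom days, with imputed dates used only where diary days are missing.

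The cost is SAP wording and a short programming step on diary data already collected. Where the diary is complete, the shift from end-date imputation becomes zero.

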18. TABLE OF CONTENTS FOR TABLES, FIGURES, AND LISTINGS

The Mock TFLs will be provided in a separate document.

19. APPENDIX

19.1 Derivations of efficacy endpoints related to angioedema attacks

The derivations of efficacy endpoints are demonstrated using the following hypothetical example.

Study Day	Symptoms Present	Maximum ^a Symptom Severity	Symptom Severity Score	Attack Number	Maximum ^b Attack Severity	Daily Severity
1	Yes	Moderate	2	1	-	2
2	Yes	Moderate	2		2	2
3	No					
4	Yes	Mild	1	2	-	1
5	Yes	Severe	3		-	3
6	Yes	Moderate	2		3	2
7	No					
8	Yes	Moderate	2	3	-	2
9	Yes	Severe	3		-	3
10	Yes	Moderate	2		-	2
11	Yes	Moderate	2		3	2

a: Maximum Severity across all anatomic locations on the corresponding study day.

b: Maximum Severity across all anatomic locations and days with symptoms for the corresponding attack.

In this hypothetical example, a patient recorded 9 days of symptoms in an 11-day study period. Because individual attacks require at least one symptom-free calendar day between episodes, this diary fragment identifies 3 angioedema attacks. The maximum severity of each attack is determined on the last day of symptoms and is derived as Mild, Moderate, or Severe. Coding these categories as Mild=1, Moderate=2, and Severe=3 and summing over the three unique attacks, yields a Cumulative Attack Severity of 8. Finally, summing the reported severity scores over the 9 days with symptoms yields a Cumulative Daily Severity of 19. With respect to these defined endpoints, this hypothetical eleven-day symptom diary would be quantitatively described by:

Endpoint	Value
Number of Angioedema Attacks	3
Cumulative Attack Severity	8
Cumulative Daily Severity	19

For the secondary efficacy variables of Cumulative Attack Severity, Cumulative Daily Severity, Number of attack-free days during a treatment period, Number of angioedema attacks requiring acute treatment during a treatment period and 98-day AAS, the normalized numbers (per month) calculated by following steps will be used in the analyses.

19.2 Derivation of normalized efficacy endpoints

Any subject who completes a treatment period should provide data with which to derive efficacy scores. Thus, for each individual treatment period, the normalized efficacy scores are calculated as below:

 X_i = Number of **days** of participation in that treatment period for Subject *i*,

 $Y_i = \mathbf{RAW}$ Efficacy Score expressing the cumulative period score for Subject *i*,

 Y^*_i = **NORMALIZED** Efficacy Score for Subject *i*, (the normalized score expressed as score

per **Month**), which is calculated as $(Y_i / X_i) * 30.4$

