8. EXTENT OF EXPOSURE AND TREATMENT COMPLIANCE

8.1 Exposure to Investigational Product

For all treated subjects, including the ones who had early termination, treatment exposure is the duration between the first dose date and last dose date in each treatment period. Average daily dose, total dose, total number of doses, total exposure, length of exposure to investigational product (<=1 wk, >1 - <=2 wk, >2 - <=5 wks, >5 - <=10 wks, >10 - <=14 wks, >14 - <=18 wks, >18 - <=24 wks, >24 - <=28 wks, >28 wks), and treatment compliance will be summarized by treatment for the Safety Set and Full Analysis Set.

A listing will be created by subject and treatment and will show the date and time of dose administration for each treatment given for the Safety Set.

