10.5.2 Multiple Imputation Analysis

Analysis based on imputing missing values by drop out reason (Protocol Section 4.4.1) are added as sensitivity analysis to the primary efficacy analysis. The primary imputation method within the sensitivity analysis will be the multiple imputation method for the Full Analysis Set described below in this section.

A subject is considered to have missing values in case he/she leaves the study prematurely. The fraction of non-missing data (f) and normalized number of HAE attacks (NNA_{observed}) will be determined per treatment period and subject as follows:

17 Aug	2017
--------	------

Category	Level of Participation per Treatment Period	Fraction of non-missing data (f) per Treatment Period	Observed normalized number of HAE attacks (NNA _{observed})
А	Subject is not discontinued from the study	1	As outlined in Section 8.1
В	Subject is discontinued from the study in a treatment period	Days of participation / scheduled length of treatment period (days)	As outlined in Section 8.1
С	Treatment period 2 among subjects who discontinued during treatment period 1	0	

Days of participation will be calculated as defined in Section 8.1 and scheduled length of treatment period is the intended length, i.e., 14 weeks for analysis equals $14 \times 7=98$ days.

The missing data will be imputed with NNA according to the sensitivity analysis by drop out reason. The normalized number of HAE attacks to be used for the sensitivity analysis (NNA_{analyzed}) will be calculated based on the observed number (NNA_{observed}) and the imputed number (NNA_{imputed}) taking into account the fraction of non-missing data (f) as:

 $NNA_{analyzed} = f \times NNA_{observed} + (1 - f) \times NNA_{imputed.}$ (Equation 10.1)

Values for NNA_{observed} will be determined as outlined in the above table; values for NNA_{imputed} will be determined for each subject and period with missing data depending on the sensitivity analysis as described below.

If a subject discontinues prematurely in treatment period 1, his/her NNA_{analyzed} value during treatment period 2 will be imputed by the median of the non-missing NNA_{observed} from all subjects who have complete data within the same treatment as that the subject is expected to take in treatment period 2.

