5.1.3 Missing Data

Frequencies will be used to evaluate missing data and measures will be scored in accordance with the instrument developers' recommendations listed below:

- AE-QoL: Domains can be calculated if no more than 1 item is missing and the total score if no more than 25% of items (> 4 items) are missing (Weller et al., 2012).
- EQ-5D-5L: Index scores cannot be calculated if any of the five dimensions is missing (Simons et al., 2015).
- EQ-VAS: EQ-VAS score cannot be calculated if the EQ-VAS is not completed at an assessment.
- WPAI GH: Scores cannot be calculated if there is a missing response to a corresponding item (Reilly Associates, 2002).
- SDS: No established conventions exist but since the Global functioning impairment score is comprised of only three items, the score will not be calculated if at least one of the three dimensions is missing.
- AAS: Total scores can be calculated so long as no more than a week (7 days) of data are missing (Weller et al., 2013).

Imputation of missing data will be limited to end of treatment data used in the calculation of change scores. In the event that a subject is missing end of treatment data, the closest available score to the period end or discontinuation will be used so long as the value was obtained a minimum of 9 weeks past the period start date. If not available, no change score will be calculated. No other missing data will be imputed.

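### SAP 19.2 divides the recorded AAS sum by all days of participation, so each unanswered AAS day is scored as zero

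*SAP*

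**What the plan says.** SAP 10.4 defines the AAS endpoint as "the normalized sum of the daily AAS during a treatment period, where the daily AAS is the sum of AAS items per day". SAP 19.1 lists it among the scores to be normalized. SAP 19.2 gives the formula: normalized score = (Y/X) × 30.4, where Y is the raw cumulative score and X is the number of days "of participation in that treatment period for Subject" i.

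Section 19.2 does not define participation further. Elsewhere the SAP measures time in a period by dosing, not by diary entries. For subjects who stop early, SAP 10.4 says that "the days of the treatment period will be the days on treatment for that subject". SAP 8.1 says that "treatment exposure is the duration between the first dose date and last dose date in each treatment period".

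Protocol 9.4 promises that the SAP will explain how missing data are treated. In the main SAP, section 17.11 deals with incomplete attack start and end dates, and section 10.5.2 imputes the NNA after premature discontinuation. Neither deals with a skipped AAS day.

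The separate HRQoL SAP does have a rule. Its section 5.1.3 states: "Total scores can be calculated so long as no more than a week (7 days) of data are missing". Its section 10.1.5 derives three AAS summaries: a period total, an overall average formed as the mean of the daily scores, and weekly averages.

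**The concern.** Protocol 7.2.2.3 has subjects enter the AAS every day, with a daily range of 0 to 15. A day answered as free of swelling is a true 0, whereas an unanswered day is unknown. Under SAP 19.2 the two are indistinguishable, because each adds 0 to Y and 1 to X.

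This has two consequences. Incomplete diaries pull every subject's rate down, which shrinks any real difference between active and placebo. If completion also depends on treatment, the estimated difference partly measures diary behaviour. Its sign then depends on which treatment has more gaps, and the plan has no tabulation of completion that would let a reader judge.

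**Working it through.** **Inputs.** The formula is from SAP 19.2, the AAS numerator from SAP 10.4, the 98-day period from SAP 10.5.2, the planned 44 crossover completers from SAP 2.5, and the 7-day limit from HRQoL SAP 5.1.3. The documents give no diary-completion rates, AAS means or AAS standard deviations, so all such values below are assumptions.

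**The plan's own figure.** There is no worked example for the AAS. SAP 19.1 gives one for cumulative daily severity over 11 days: 2+2+1+3+2+2+3+2+2 = 19, which matches. SAP 19.2 then gives 19/11 × 30.4 = 52.5 per month. It serves here only to show the arithmetic of a gap:

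- One Severe day unrecorded, divided by 11: 16/11 × 30.4 = 44.2. Divided by the 10 completed days: 16/10 × 30.4 = 48.6.
- One symptom-free day unrecorded, divided by 11: still 52.5, which is correct. Divided by 10: 19/10 × 30.4 = 57.8, which is too high.

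**General form for the AAS.** Let m be the true mean daily AAS and c the fraction of days completed. If missed days resemble completed days:

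- as written, expected normalized score = 30.4 × m × c;
- divided by completed days, expected normalized score = 30.4 × m.

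**Equal completion in both periods.** The difference becomes c × 30.4 × (m_active − m_placebo). With c = 0.90, 10% of the true difference is lost. With true means of 1 and 2 points per day the true difference is −30.4 per month; at c = 0.80 it becomes −24.3.

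**Unequal completion, no true effect.** With 85% on active and 95% on placebo, the ratio is 0.85/0.95 = 0.895, a false advantage of 10.5%. In points at m = 2, this is 30.4 × 2 × (0.85 − 0.95) = −6.1 per month. A wider gap of 80% against 95% gives:

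| Assumed m | False difference per month |
|---|---|
| 1 | −4.6 |
| 2 | −9.1 |
| 4 | −18.2 |

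A simulation of 44 subjects over 98 days at about m = 2 gave −9.12 as written and −0.01 after dividing by completed days. For scale, the 7-day minimal difference of 8 in HRQoL SAP 4.2.5 is 8/7 × 30.4 = 34.7 per month.

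**Chance of a false finding.** Take m = 2, 80% against 95%, n = 44, and an assumed SD of the within-subject difference of 30, 45 or 60. The one-sided 0.025 error rate, Φ(9.12/(SD/√44) − 1.96), becomes about 0.52, 0.27 or 0.17.

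**Unequal completion hiding an effect.** With true means of 1 on active (95% complete) and 2 on placebo (60% complete), 30.4 × 0.95 − 60.8 × 0.60 = −7.6, against a true −30.4.

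**If the 7-day limit were applied to this endpoint.** The loss per period is at most 7/98 = 7.1%. At m = 2 the largest false difference is 4.3 per month, and the error rate for the same three SDs is 0.16, 0.09 or 0.07. The limit bounds the problem but does not remove it.

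**The case against.** Several objections have force.

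*Other daily endpoints.* A reader might infer that cumulative daily severity and attack-free days are biased in the same way. The documents do not support that. Under Protocol 7.2.2.2 the investigator completes an attack CRF with onset, resolution and severity, and SAP 17.11 imputes incomplete attack dates, so an attack that spans an unanswered day may still be known. The SAP does not name the source for these endpoints. If only days recorded as symptom-free counted as attack-free, gaps would make a subject look worse.

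*HRQoL analyses.* A reader might infer that the HRQoL AAS results share the bias. In HRQoL SAP 6.4.1 the models and responder analyses use the final week's average daily score. The unscaled total appears only in a descriptive table beside the daily average. The two AAS totals also differ in scale by design, one per month and one a 98-day sum; what remains unreconciled is the missing-day rule.

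*Meaning of participation.* The SAP 10.5.2 sentence, "Days of participation will be calculated as defined in Section 8.1", concerns the NNA imputation, so it does not define X in 19.2. It shows only how the SAP uses the phrase elsewhere. The point stands under any calendar-time reading.

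*Blinding and period adjustment.* The trial is double-blind and the model includes period. A decline in completion over time that is the same on both treatments does not create a difference. With equal sequence sizes the estimate is (m_active − m_placebo) × 30.4 × (c1 + c2)/2, where c1 and c2 are completion in periods 1 and 2. Completion of 95% then 80% costs 12.5% of the effect and adds no false one. This objection stands: a false difference needs completion to differ by treatment.

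*The remedy.* Dividing by completed days overcorrects if subjects mostly skip quiet days. This also stands, and the fix allows for it.

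The opening of SAP 10.5.1 is missing from the text available to me, so I cannot exclude a relevant sensitivity analysis there.

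**Conclusion.** The point holds for the normalized 98-day AAS. The formula as written scores an unanswered day as 0. Equal incompletion shrinks a true difference in proportion: 10% missing in both periods costs 10%. Completion that differs by treatment creates or hides a difference, for example a false 10.5% advantage at an assumed 85% against 95%. These sizes assume that missed days resemble completed ones. Nothing in the documents shows that completion will differ by treatment, so the direction and size of any actual bias are unknown.

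The stakes are moderate. Under SAP 10.3 the AAS is outside the ordered tests, and study success rests on the primary endpoint alone. The plan should still change: the AAS is a named secondary endpoint with a model-based treatment comparison. The sponsor already uses the better principle elsewhere, both in the mean of daily scores in HRQoL SAP 10.1.5 and in SAP 19.3, which divides by non-missing items for the AE-QoL.

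**What to change.** 1. In SAP 19.2 and 10.4, for the AAS only, set X to the number of days in the period with a completed AAS entry. This equals 30.4 × the mean daily AAS and agrees with HRQoL SAP 10.1.5.
2. Keep the zero-scored version as a sensitivity analysis, because the new divisor overcorrects if missed days were mostly symptom-free.
3. Apply one missing-day limit in both SAPs, and say whether it is counted over time on treatment or over all 98 days, which matters for subjects who stop early.
4. Tabulate diary completion by treatment and period.
5. For cumulative daily severity and attack-free days, state the source (diary or attack CRF dates) and how an unreported day is classified. Do not change their denominator by default.

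The cost is SAP wording, one derived variable and one table, all from diary data already collected. Trial conduct and the primary analysis are unaffected. Protocol 9.4 requires the SAP to be final before unblinding, so this should be settled by then.
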